### Survey Details

2-4 weeks after randomization, the patient will receive a phone call from a member of research staff to conduct a brief 5-10 min survey to assess gastrointestinal side effects of iron supplementation and compliance. Patients will be made aware of this survey in the consenting process. Study subjects will then resume standard prenatal care visits.

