### Secondary outcomes:

- Assessment of GI adverse effects determined by survey
- Analysis of CBC indices including reticulocyte count, MCV, etc.
- Iron studies at time of diagnosis
- Need for parental iron supplementation
- Need for transfusion in the peripartum period
- Postpartum hemoglobin and hematocrit
- Neonatal weight
- Presence of antepartum fetal growth restriction
- Neonatal outcomes such as NICU admission, hyperbilirubinemia, and APGAR scores
- Relationship of obesity to effectiveness of supplementation in both study arms

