## 3. Concise Summary of Project:

This trial will be a comparative pragmatic open label randomized controlled trial of daily versus alternate day dosing of oral iron in anemic pregnant patients.

Two randomly assigned groups will be compared during the antepartum period:

- 1. Control Group: standard of care, daily oral iron supplementation (325 mg PO daily ferrous sulfate)
- 2. Intervention Group: alternate day dosing oral iron supplementation (650 mg PO every other day ferrous sulfate)

325mg Ferrous sulfate is a standard oral iron supplement providing 65 mg of elemental iron per dose. Standard dosing recommendations for the treatment of iron deficiency anemia is between 65 to 200 mg elemental iron daily.

Each group will receive a phone survey 2-4 weeks after initiation of therapy to assess side effects of each group as well as compliance. Call is anticipated to last approximately 10-15 minutes. This survey has previously been validated in assessing gastrointestinal symptoms for those taking oral iron supplementation (33).

The number of subjects studied will be 86 subjects at UTMB, we plan to approach and consent up to 96 patients to allow for screening failures, early withdrawals, and patients lost to follow-up, and patients who must withdraw due to failure of therapy. Failure of therapy for the purposes of this study will be patients who require parental iron supplementation or transfusion. Study to last an anticipated length of 3 years. If our sample size is not achieved, we will submit to the IRB an addendum to increase the number of consented subjects to achieve the desired sample size.

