#### Research Team

The research team (or research staff) will consist of the PI, faculty sponsor, trained research coordinator, and additional staff to be trained and added to the research protocol. All members of the research team will be able to screen and consent subjects. Physician research team members will be responsible for providing the prescriptions to patients who agree to take part in this study. The PI and faculty sponsor will work together to ensure that the team is of sufficient size to carry out the project. Consenting and enrollment of subjects will only occur when a research team member is physically present at a study location.

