#### Screening

All pregnant patients undergo a laboratory screen for anemia at the first prenatal appointment as part of the UTMB standard of care. Eligible patients (1st or 2nd trimester patients with a hemoglobin below 11 g/dl or 10.5 g/dl respectively) will be screened and approached at their next prenatal appointment for consent (detailed under section 9). We request a waiver to screen these patients.

The anticipated procedures flow is as follows

- 1. Research staff will travel to location
- 2. Research staff will confirm with provider that possible subjects are appropriate candidates for treatment with ferrous sulfate
- 3. Research staff will approach screened patients to obtain consent from possible subjects
- 4. Subjects will be randomized using a randomization log with group assignment, subject name, and medical record number
  - a. Daily dosing group will take ferrous sulfate 325 mg (65 mg elemental iron) by mouth daily
  - b. Alternate day dosing group will take ferrous sulfate 650 mg (130 mg elemental iron) by mouth every other day
- 5. Prescriptions for the appropriate regimen will be provided by the research staff
  - a. If the research staff is a physician, the appropriate prescription will be sent at time of encounter
  - b. If the research staff is a non-physician, a physician research staff member will be alerted and the appropriate prescription will be sent on the same day
- 6. After patient is consented and enrolled, the provider will be notified and a note will be placed in the electronic chart indicating that the patient is enrolled in the study.

- 7. Subjects will continue to receive standard, routine prenatal care and surveillance of iron deficiency anemia in pregnancy
  - a. Research staff and PI will monitor surveillance data by chart review
- 8. 2-4 weeks after initiation of respective iron regimen research staff will contact subjects by phone to administer a 5-10 min survey to assess GI side effects and compliance with regimen.
- 9. Research staff will conduct chart review to obtain the datapoints for the primary and secondary outcomes (described in section 1)

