## 13. Potential Benefits:

The potential benefits of the study to the intervention group (alternate day dosing) include:

- 1. Improved fractional absorption of iron with corresponding improvement of anemia compared to standard oral iron replacement therapy
- 2. Decreased GI side effects with alternate day dosing

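### The GI symptom survey is administered by the unblinded team that assigns and teaches the regimen, with compliance in the same call, which leaves an avoidable interviewer bias of unknown size in a secondary outcome

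*Combined protocol and SAP*

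**What the plan says.** All references are to the combined protocol and SAP.

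- Section 3 describes the design: "This trial will be a comparative pragmatic open label randomized controlled trial". No section provides for a blinded or independent outcome assessor.
- Section 1, Secondary outcomes lists "Assessment of GI adverse effects determined by survey". Section 13 gives, as the second potential benefit to the intervention group, "Decreased GI side effects with alternate day dosing".
- Section 4, Research Team: "All members of the research team will be able to screen and consent subjects".
- Section 4, Screening, steps 4 and 5: "Subjects will be randomized using a randomization log with group assignment, subject name, and medical record number", and "Prescriptions for the appropriate regimen will be provided by the research staff". Section 9 adds that the staff member taking consent also teaches the woman her dosing regimen.
- Section 4, Screening, step 8 has research staff telephone at 2-4 weeks to "administer a 5-10 min survey to assess GI side effects and compliance with regimen". Survey Details repeats this: "the patient will receive a phone call from a member of research staff to conduct a brief 5-10 min survey".
- Two features count in the plan's favour. Section 3 says the survey has been validated for GI symptoms in people taking oral iron. Section 9, Spanish speakers says surveys will be translated, which implies a fixed written text.

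**The concern.** The woman and her provider must know the regimen in this design, but the person who telephones her need not. As written, the caller may be the person who enrolled her, explained the regimen or sent the prescription. A question about adherence to a daily or an every-other-day schedule also tends to disclose the arm to a caller who did not know it.

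The outcome is subjective, and the team has grounds to expect a particular answer. Section 13 names fewer GI effects as a potential benefit, and Section 2 cites a trial in iron-deficient anemic women with fewer GI side effects on alternate days. Prompting, clarifying and recording of symptoms over the telephone could then differ between arms.

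The result may matter in practice. Section 4, Outcomes hypothesises that alternate-day dosing is superior or at least not inferior on hemoglobin. If hemoglobin proves only non-inferior, tolerability would be a natural reason to prefer one regimen. That is a judgement about how the results would be used; the plan does not say it.

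**Working it through.** The plan gives no GI event rate, effect size or power, so there is no figure to reproduce. The check is mainly a comparison of the sections.

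**1. Can the caller know the arm before dialling?** Yes. The caller comes from research staff (Survey Details). Every team member may screen and consent (Research Team). Staff randomise from a log that shows the group beside the name and supply the prescription (Screening), and they teach the regimen (Section 9). No rule separates these roles from the call.

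**2. Can the call itself disclose the arm?** Yes. GI effects and compliance share one call. Both Screening and Survey Details name GI effects first, but neither sets an order or requires GI answers to be recorded before compliance is raised.

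**3. Is the outcome open to interviewer influence?** To a limited degree. The symptoms are the woman's own report and staff administer a validated instrument. That narrows the room for influence. It does not conceal the arm, and the protocol does not say that items are read as written.

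**4. Does it reach the primary outcome?** Not by this route. Hemoglobin and hematocrit are laboratory values taken in routine care.

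**5. How sensitive would a GI comparison be?** The following rests on assumptions and shows vulnerability only.

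- Inputs from Section 14: 86 enrolled, so 86/2 = 43 per arm if allocation is equal; 39 per group evaluable (planned for hemoglobin, borrowed here); Pearson chi-square; P < 0.05.
- Assumed: GI symptoms reduced to one yes/no result, no true difference, average recorded rate p of 20% to 50%, and a gap k between arms due only to recording.
- Formula: recorded rates are p + k/2 (daily) and p − k/2 (alternate-day). The test rejects when (p̂₁ − p̂₂)² / [p̄(1 − p̄)(2/n)] exceeds the 5% chi-square limit on 1 degree of freedom. Binomial probabilities are summed over all pairs of counts that reject in favour of alternate-day dosing.

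| Assumed gap k | 43 per arm | 39 per arm |
|---|---|---|
| 0 points | 2-3% | about 3% |
| 5 points | 6-9% | 7-8% |
| 10 points | 14-22% | 15-20% |
| 15 points | 27-43% | 27-39% |
| 20 points | 45-67% | 44-62% |

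A small gap does little, while a large one would often yield a nominally significant result. Nothing in the documents says which row applies, or how any gap would divide between interviewer and patient.

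**The case against.** The strongest reply is that the trial is openly declared open label and that, for self-reported symptoms, the unblinded woman is herself the assessor. Nothing in the documents separates interviewer bias from her own expectations, so the gain from an uninformed caller is unknown. This stands, and it limits the claim. It does not justify leaving in place a second source of bias that can be removed.

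The validated, written questionnaire also stands as a real safeguard. Staff administer it; they do not rate symptoms themselves.

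A reader might infer more than the text supports:

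- *That the enrolling person makes the call, or that the caller always knows the arm.* The text permits both and states neither.
- *That compliance questions disclose the arm before GI symptoms are recorded.* The order is not stated, and GI effects are named first.
- *That the bias must favour alternate-day dosing.* That direction is plausible from Sections 2 and 13 but not shown. Section 10, Randomization Risk allows that either group may have fewer side effects, and women taking 650 mg at once, against 325 mg, could expect more upset.
- *That the size can be stated.* Any assumed gap only returns itself. With recorded rates of 45% and 35% at 43 per arm, z = 0.10/√(0.40 × 0.60 × 2/43) = 0.95, p about 0.34, so a 10-point observed gap would not reach significance.
- *That the recall period is unsuitable for alternate-day dosing.* The questionnaire is not in the documents, so this cannot be judged.

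**Conclusion.** The concern holds as a gap in outcome assessment. One unblinded team assigns, teaches and prescribes the regimen and administers the GI survey. Compliance is asked in the same call, and no provision keeps the caller unaware of the arm or fixes the order of questions. Interviewer bias can therefore add to the patient-side bias that the design cannot avoid. Its size is unknown and its direction is only plausible. The table above describes assumed gaps and is not an estimate.

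The reach is limited to one secondary outcome among ten, already partly protected by a validated instrument. The conclusion rests on what the protocol leaves open; actual conduct may be better than the text requires. The change is worth making because it is inexpensive and because tolerability could influence how a non-inferior hemoglobin result is read.

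**What to change.** Amend Section 4, Screening (step 8) and Survey Details to state that:

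1. The call is made by an existing team member who did not consent, teach, randomise or prescribe for that woman. The caller works from a call sheet without the assignment and does not open the randomization log or her chart beforehand.
2. The validated GI items are administered as written, with the questionnaire's own recall period, and the answers are recorded before any compliance question is asked.
3. The GI result is reported as open-label, patient-reported data, with a plain statement that women knew their regimen.

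This takes protocol wording, a call script in fixed order, and allocation of calls within the team, which Section 4, Research Team already undertakes to keep at sufficient size. No visit, blood draw or dosing change is involved. The price is less flexible scheduling, which a small team will notice because the same staff also keep the log and review charts. Bias from the woman's own knowledge of her regimen remains.

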#### Additional details

The routine prenatal visits for pregnant patients with anemia include at least monthly venipunctures to monitor the treatment of anemia and intervene if necessary. Our primary outcome of 3rd trimester hemoglobin as well as laboratory secondary outcomes are convenient data points collected in the standard treatment and surveillance of anemia in pregnancy. As such patients will not need any study specific venipuncture or visits. Prenatal visits are frequent with monthly visits in the 1st trimester, bi-monthly visits in the 2nd trimester, and weekly visits in the 3rd trimester with 24 hour after hours care phone services available. The frequency and ready availability of appointments ensures that any symptomatic patient will quickly be seen and evaluated.

Any subject that requires escalation of treatment beyond oral supplementation (IV iron infusion or blood transfusion) will be referred to receive appropriate intervention. These subjects will still be included in the intent-to-treat analysis. The routine surveillance of anemic pregnant patients described above ensures that any treatment failure will be quickly identified and addressed.

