#### Brief Study Design and Rationale

Two randomly assigned groups will be compared during the antepartum period:

- 1. Control Group: standard of care, daily oral iron supplementation of ferrous sulfate 325 mg (65 mg elemental iron) taken by mouth once daily.
- 2. Intervention Group: alternate day dosing oral iron supplementation of ferrous sulfate 650 mg (130 mg elemental iron) taken by mouth every other day.

Historically twice or thrice daily oral iron supplementation has been the recommended as the first line treatment of iron deficiency anemia. This standard of care for oral iron therapy is starting to change (1, 2) with some current textbooks and guidelines recommending either daily or every other day dosing regimens (3, 4). The standard of care at UTMB for the detection and treatment of iron deficiency anemia is as follows. All pregnant patients undergo blood draws at their first appointment for anemia screening. Those patients who are identified as anemic then undergo further studies to determine the type of anemia. Those patients determined to have iron deficiency anemia receive oral iron supplementation. There are many different iron supplements that are used at UTMB to treat iron deficiency in pregnancy. These supplements vary in elemental iron content, enteral coatings, and supplements combined with vitamins and minerals. The choice of which iron supplement that patients receive is left to the discretion of the provider caring for the patient. Among these choices, ferrous sulfate (325mg, with 65mg elemental iron) is very commonly prescribed to UTMB patients and thus is the oral iron therapy that will be used for this study. Standard UTMB treatment surveillance includes blood draws at least every trimester or more frequently based on symptomatology of patient and provider discretion. This study will follow the UTMB standard treatment surveillance protocol and thus study participants will have no study specific blood collections. As part of this standard surveillance if hemoglobin levels remain low patients may be considered for more aggressive treatments such as IV iron infusion or transfusion. The decision to escalate treatment takes into account risk of cesarean delivery and risk of obstetric hemorrhage among other considerations and will be left to the discretion of the provider.

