## 14. Biostatistics:

We hypothesize that the intervention group will have a higher hemoglobin level in the third trimester than the standard group. The primary analysis will be conducted on an intention-to- treat basis. Between-group differences in continuous variables, will be assessed using Student t test or Man-Whitney rank sum test and results will be given as mean, standard deviation or median range as appropriate. Categorical variables will be assessed using the Pearson chi-square test or Fisher exact test as appropriate. For dichotomous endpoints, relative risk (RR) and 95% CI values will be calculated. P <0.05 will be considered significant. The analysis will be performed after study completion.

Based on our historical data at our center of 56 anemic women with iron deficient anemia that received standard daily iron supplementation: third trimester hemoglobin mean of  $10.27 \pm 1$  g/dL. We will first do a noninferiority approach. If noninferiority is not met, we will do a superiority analysis. For the noninferiority: If there is truly no difference between the standard and experimental treatment, then 68 subjects will be required to be 90% sure that the lower limit of a one-sided 95% confidence interval (or equivalently a 90% two-sided confidence interval) will be above the non-inferiority limit of -1. For the superiority: We estimate that a minimum sample of 39 per group, total N= 78 women will be needed to provide a power of 90% with a two-sided alpha level of 0.05 and a 1 g/dL difference in hemoglobin between control and intervention. We plan to enroll 86 patients in order to account for up to 10% missing data or loss to follow up. If no differences are noted among groups (non inferiority hypothesis failed) we will be performing a superiority approach. Stata 16 will be used for the statistical analysis.

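### The plan does not say which hemoglobin counts after IV iron or transfusion, and it conflicts on whether rescued women stay in; if alternate-day dosing is worse, this can favour the non-inferiority claim.

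*Combined protocol and SAP*

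**What the plan says.** **Retention.** Section 4 (Additional details), on women who need IV iron or transfusion: "These subjects will still be included in the intent-to-treat analysis". Section 14: "The primary analysis will be conducted on an intention-to- treat basis".

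**Withdrawal.** Section 3, explaining why up to 96 women will be consented, includes "patients who must withdraw due to failure of therapy". It then defines the term: "Failure of therapy for the purposes of this study will be patients who require parental iron supplementation or transfusion".

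**What prompts escalation.** Section 1 (Brief Study Design and Rationale): "if hemoglobin levels remain low patients may be considered for more aggressive treatments such as IV iron infusion or transfusion". No hemoglobin threshold is given. The decision weighs delivery and hemorrhage risks "among other considerations and will be left to the discretion of the provider".

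**Blinding.** Section 3 describes a "comparative pragmatic open label randomized controlled trial". Under section 4 (Screening) the provider is told of enrolment and a chart note is placed.

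**Endpoint.** Section 4 (Additional details): "Our primary outcome of 3rd trimester hemoglobin as well as laboratory secondary outcomes are convenient data points collected in the standard treatment". No week is fixed, no rule chooses among several values, and nothing says whether a rescued woman's value comes before or after rescue.

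**Test.** Section 14 starts with non-inferiority, limit -1, using a one-sided 95% confidence limit. It names no per-protocol or other supporting analysis. Need for parenteral iron and for peripartum transfusion are secondary outcomes in section 1.

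**The concern.** Rescue is prompted by low values of the primary outcome variable, is meant to raise that variable, and is chosen by staff who can know the arm. Suppose alternate-day dosing is worse, a risk that section 10 (Persistence of anemia) itself names. More women in that arm stay low and more are rescued. If their post-rescue values are analysed, the arm's mean is lifted by a treatment other than the assigned regimen. If they are removed, as section 3 may imply, the arm loses its lowest values. Both move the difference toward zero.

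In a superiority test that would weaken the claim. In the non-inferiority test it helps the claim. The trial could then report that alternate-day dosing is not inferior because rescue made up the deficit, with the excess rescue visible only among the secondary outcomes.

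**Working it through.** **The plan's own figure.** Section 14 gives 68 women in total for non-inferiority. With its stated inputs (SD 1, limit 1, true difference 0, one-sided 0.05, 90% power), n per arm = 2 × (1.645 + 1.282)² × 1² / 1² = 17.1. That rounds up to 18 per arm, 36 in total. The figure of 68 needs an SD of about 1.4. Likewise, 39 per group for superiority needs an SD of about 1.35. This is a separate matter, but it is why a larger SD is shown below.

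**Inputs from section 14.** Control mean 10.27, SD 1, n = 39 per arm, limit -1. The true oral-only difference is set at the limit, so the alternate-day mean is 9.27 and a correct test should declare non-inferiority 5% of the time. Section 14 states its hypothesis and SD for third-trimester hemoglobin, so that level is used.

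**Assumptions.** The documents give no trigger, rescue rate or hemoglobin gain. All three are assumed and varied.

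**Closed form.** Let e be the excess share rescued in the alternate-day arm and g the gain per rescued woman. The expected difference becomes -1 + e·g, and

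P(declare non-inferiority) = Φ( e·g / (SD·√(2/n)) − 1.645 ), with √(2/39) = 0.2265.

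Example: e = 0.10 and g = 1.5 give a difference of -0.85, and Φ(0.15/0.2265 − 1.645) = Φ(−0.98) = 16%.

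| Excess rescue | SD 1, gain 1 to 2 g/dL | SD 1.4, gain 1 to 2 g/dL |
|---|---|---|
| 0 points | 5% | 5% |
| 5 points | 8–11% | 7–9% |
| 10 points | 11–22% | 9–16% |
| 20 points | 22–55% | 16–35% |

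**Rescue tied to a low value.** Take a trigger of 8.5 and a gain of 1. Shares rescued are Φ(8.5 − 9.27) = Φ(−0.77) = 22% and Φ(8.5 − 10.27) = Φ(−1.77) = 4%. The difference becomes -1 + 0.18 = -0.82, and the closed form gives Φ(0.182/0.2265 − 1.645) = 20%. Simulation gives 24%, because raising the lowest values also narrows the spread and hence the interval.

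Simulated false non-inferiority (20,000 trials per setting, 39 per arm, every rescued woman's value taken after rescue):

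| Assumed rescue | SD 1 | SD 1.35 |
|---|---|---|
| None | 5% | 5% |
| All below 7.0, gain 1 | 5% | – |
| All below 7.5, gain 1 | 7% | – |
| All below 8.0, gain 1 | 11% | 12% |
| Half of those below 9, gain 1 | 18% | 12% |
| All below 8.5, gain 1 | 24% | 18% |
| All below 9, gain 1.5 | 83% | 52% |

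The last row needs 39% rescued against 10%.

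**If some values precede rescue.** Suppose half of rescued women are sampled before rescue and the triggering value correlates 0.6 with the outcome. At SD 1 the 8.5, half-below-9 and all-below-9 settings then give 11%, 10% and 25%.

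**If rescued women are dropped.** At trigger 8.5 and SD 1 the remaining means are 10.27 + 0.083/0.962 = 10.36 and 9.27 + 0.297/0.779 = 9.65, a difference of about -0.71. Simulated false non-inferiority in the same three settings is about 40%, 16% and 68%. Reading section 3 as removal therefore does not cure the problem.

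**The case against.** The strongest reply is that a pragmatic trial may properly count whatever happens after assignment. Keeping escalated women with their observed outcome is a recognised treatment-policy choice, and section 4 states the retention openly. That stands: retention is not the fault. What is missing is a statement that this is the intended question for a non-inferiority claim about oral regimens, and any supporting analysis that shows how far rescue carried the result.

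A reader might infer that the plan prescribes post-rescue values. It does not; it is silent. With the frequent draws that section 4 describes, a pre-rescue third-trimester value may exist for some women. Withdrawal in section 3 might also mean stopping study treatment only, but the text does not say so.

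A reader might also infer that poor responders can be moved to another oral product or to daily iron without record. The documents do not support that. The sentence in section 1 on provider choice of product describes usual practice at the center. The same paragraph fixes ferrous sulfate for the study, and section 4 has research staff prescribe the assigned regimen. Outcomes come from chart review, and compliance is asked about at 2–4 weeks.

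The size rests on assumed inputs, and with rare rescue it is negligible. The direction is conditional too: excess rescue in a worse daily arm would work against the intervention. But an inferior alternate-day arm is the case a non-inferiority test exists to catch. Finally, section 14 already provides RR with 95% CI for dichotomous endpoints, so reporting escalation by arm asks mainly for placement and an antepartum definition.

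**Conclusion.** The concern holds as a gap and a contradiction. Sections 3 and 4 disagree on whether rescued women leave or stay, and no section defines which hemoglobin represents them. Under either reading, if alternate-day dosing is truly worse and its women are rescued more often, the first-tested claim is favoured.

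With 39 per arm, SD 1, a true difference of -1 and post-rescue values analysed, false non-inferiority runs from about 5% (trigger 7.0) through 11% (8.0) and 24% (8.5) to 83% (all below 9, gain 1.5), against a nominal 5%. It is lower where some analysed values precede rescue. Trigger, rescue share and gain are assumptions throughout, so the range shows what the silence allows and does not forecast this trial. The documents do not support saying that the plan chose post-rescue values, or that intention to treat is wrong here.

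**What to change.** 1. Reconcile section 3 with section 4 (Additional details) so that every randomised woman stays in the intention-to-treat analysis, and say what withdrawal for failure of therapy means for follow-up and analysis.
2. In the existing chart review, add three fields for any antepartum IV iron or transfusion: date, reason, and last hemoglobin before it.
3. In section 14, prespecify a supporting analysis of the non-inferiority comparison that uses the last pre-escalation hemoglobin for these women. State that a non-inferiority conclusion will be interpreted together with that result.
4. Report the antepartum escalation proportion by arm (RR, 95% CI) beside the primary result, and report transfusion for delivery bleeding separately.

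The cost is three data fields and one analysis. No visit, blood draw or clinical escalation decision changes. The rule should be written before outcome data are compared by arm, since one chosen later would carry little weight.

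The downside is that pre-escalation values come earlier in pregnancy and are selected at a low point. The analysis is therefore conservative against the arm rescued more, and should support the primary analysis rather than replace it.
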